4.2 Peer Coaches

Peer Coach Recruitment

Peer coaches are individuals with RA who will be community member consultants in the study. Peer coaches are not health professionals but individuals who have RA. They will be trained in motivational interviewing, basics of communication, goal setting, and the PALS educational materials for the study. Peer coaches will complete a 7-week study protocol training led by [name] with support from the study research team.

Peer coaches are recruited by 2 methods:

1. ArthritisPower, our collaborator, will identify candidates who they believe would be good peer coaches based on their leadership and experience within the online arthritis community.
2. [name] will also identify patients from her own rheumatology practice who would be suitable candidates.

Peer Coach Screening

After an individual is referred, a research assistant will assess if the candidate meets the following inclusion criteria:

- Have RA

- Patient should provide the RA medications (DMARDs) prescribed to them in order to meet criteria as having RA.
- Speaks English
- ≥ 40 and ≤ 75 years of age
- Taking a statin OR had a cholesterol test within the last 2 years
- Willing to have a cholesterol test if they have not yet been tested
 - This means that during training to become a peer coach, the potential peer coach would then need to have a cholesterol test done and a cardiovascular risk assessment done. This only applies to potential peer coaches who have not had a cholesterol test within the last 2 years or are not taking a statin.
- Willing to become a peer coach and discuss with peers' aspects about RA and CVD risk
- Have internet access
- Have a phone
- Express interest in helping others with RA
- Resides or lives in the US

After screening, the principal investigator and research study team will meet to review and discuss each candidate.

- If the candidate is not asked to move forward to be trained, the reason is documented. These individuals will be notified by the research assistant.
- If the individual is considered to be a good candidate, but is unavailable for the scheduled training, permission is obtained from the individual to contact them for future programs.
- Individuals who are considered a good candidate to be a peer coach will be scheduled for an upcoming training.

Peer Coach Training

Groups of 4-8 peer coaches will be scheduled for online training meetings. The peer coaches will be part of the research team that will be conducting this study and will be considered community member consultants. There will be a total of 7 group web conference training sessions via Zoom over 2 months. At the first meeting, peer coaches will be introduced to the CARE RA intervention schedule (Table 3). Over the course of training, the research team will review each chapter of the Peer Coaches' manual to teach the activities that the peer coach will need to complete throughout the intervention. Frequently asked questions (FAQs) are included that will help peer coaches manage various situations that may arise with their client.

During each online group training meeting, the following activities will occur:

- Review of learning materials on PALS
- Review of Peer Coach Manual (each week's session calls will be scripted in these manuals)
- Didactic training in motivational interviewing skills
- Practice of motivational interviewing skills

Group web conferences will be supplemented by 2 motivational interviewing (MI) training sessions on zoom with the PI and/or research assistant and only two coaches. During these smaller MI

sessions, peer coaches will practice MI skills with reinforcement by the PI and/or research assistant. During each MI training session, the following activities will occur:

- Practice of motivational interviewing skills by each peer coach, using role-play scripts and alternating roles between coach and subject under the supervision of the PI and/or the research assistants of the study
- Reinforcement of skills in real-time with encouragement of peer coaches to critique each other's skills

Group training sessions will be accompanied by paired practice sessions. Each coach will be paired with another coach. They will be asked to listen to the PI and/or research assistant delivering each session to a mock subject on audio recordings. They will then each practice delivering the intervention session in turn to their partner. Each coach in training will be encouraged to critique their partner's performance based on MI skills learned earlier in training. If coaches do not feel confident that they have mastered a session, they will be encouraged to continue to practice with their partner. Once each coach feels confident, they will schedule a separate one-on-one certification session with the PI and/or research assistant. At this session the PI and/or research assistant will play the role of the subject and the coach will deliver the session. The PI and/or research assistant will use a checklist to assess proficiency. Each coach will be certified on each session separately. If needed, additional training can be scheduled until each coach reaches the minimum level of proficiency. Only those that pass all the certification sessions will be allowed to work with subjects in the study.

Peer Coach Retention

Retention activities consist of the following:

- Ensure timely payment for work
- Provide ongoing support and continuing education/retraining with opportunities for practicing skills
 - Weekly group conference calls to assess process measures and monitor progress of the intervention
 - Provide group problem-solving for challenges encountered
 - Provide emotional support
 - Build group identity and pride
- Allowing each coach to determine their workload, increasing or decreasing according to life demands
- Be respectful of peer coaches' time and schedules
 - Keep mandatory conference calls and individual calls on time, short as possible, and reschedule only if necessary.
 - Provide assistance as needed in scheduling sessions with subjects

4.3 Patient Activated Learning System (PALS)

The PALS is a publicly available educational and empowerment resource designed to provide engaging, easily understood, and well-researched facts for people who want to know more about health, medicines, and diseases. PALS was developed at Weill Cornell Medicine Division of General Internal Medicine where its content is developed and curated (www.palsforhealth.com). The content in the PALS is evidence-based and peer reviewed. This content is translated into

patient-facing text in plain language, aiming for a sixth-grade reading level. Content is accompanied by visuals or short videos to reinforce the single learning objective for each module, known in the PALS parlance as a renewable knowledge object (RKO). Each RKO includes an assessment question about the information that they just reviewed. The PALS is based on Adult Learning Theory and Bandura's Social Cognitive Theory, informed by Bartell's Taxonomy of online interactions types.

The educational material of CARE RA will be posted on the PALS platform and clients can access it as many times as they want. Each session of the CARE RA curriculum is tied to several PALS RKOs that clients are asked to view ahead of their discussion with the peer coach. Subjects in the self-administered learning arm of the study will be given the complete list of these same PALS RKOs to view on their own.

4.4 Intervention Mapping

CARE RA is a behavioral intervention with the goal of increasing activation and self-efficacy in individuals with RA to participate in their own care. A theoretical framework maps a causal relationship between a problem and the factors contributing to it, while identifying modifiable factors that can enable behavioral change.

Table 1: Intervention Mapping to Social Cognitive Theory

Theoretical Construct	Targeted Barrier	Intervention Activity	Corresponding Session
Self-Efficacy	Feeling isolated Lack of understanding of CVD risk Lack of understanding of the effects of RA systemically Lack of understanding of the value of having a PCP	Education (PALS), Coaching, Motivational Interviewing (MI), Empowerment	Sessions 1, 2, 3 Learn More modules
Outcome Expectation	Unrealistic expectations about the goals for RA disease control Unrealistic expectations about CVD risk Unrealistic expectations that because they ask for a cholesterol test, that the doctor will order it Fear of need to take another medication	Education, Action planning, MI,	Sessions 2, 3, 4, 5 Learn More modules
Socio-Cultural Factors	No resources to learn from about CVD No guidance of how to engage in healthy behaviors (e.g. healthy diet, regular exercise, take medications) Disruptive social support (e.g. family preference for unhealthy diet, preference for junk food over healthy food) Lack of understanding of CVD risk	Supportive coaching, Action planning, Education (PALS)	Session 2, 3, 4, 5 Learn More modules

MI = motivational interviewing; CVD = Cardiovascular Disease; PCP= Primary Care Provider.

5. STUDY POPULATION

5.1 Study population

Inclusion Criteria

- Have RA
- Age between 40 and 75 years (inclusive)

- Provide a date of their next appointment with their rheumatologist or other physician on their care team
- Willing to work with a peer coach
- Speaks English
- Have a phone
- Has access to the internet
- Resides or lives in the US

Exclusion criteria

- Do not have RA
- Younger than age 40 or older than age 75
- Taking a statin
- Known history of diabetes.
- Known history of CVD defined by:
 - Open heart surgery
 - Coronary angioplasty
 - History of heart failure
 - History of heart attack or stroke

Participants will be screened using a REDCap screening survey. If participants answer yes to any of the exclusion criteria questions, the survey skips to the end, and participants will be informed that they are not eligible. The age range for the inclusion criteria reflects the age range of the current AHA guidelines for risk assessment for CVD. The exclusion of established CVD reflects differences in national guidelines on the management of patients with established CVD vs. preventing CVD. The overall goal of this research is to discover effective strategies to prevent CVD, therefore we focus here on primary prevention.

5.2 Study duration

The study duration will be a maximum of 18 weeks from baseline enrollment to final follow up at 3 months after enrollment. The duration of the intervention is 5 weeks (Figure 2 and Table 2).

5.3 Planned number of subjects

We plan to enroll 128 subjects into this study. We will recruit patients from the ArthritisPower Patient Powered Research Network (PPRN), the Bendcare patient network, [name] practice at New York Presbyterian – Brooklyn, and social media using Twitter. We will also be recruiting participants using flyers created by a company (BuildClinical). These flyers will be posted online and interested participants will be referred to us. The PPRN has over 28,000 patients with arthritis throughout the United States and territories. In order to enroll this number of subjects, it is expected that approximately 180 subjects will be screened. This takes into account an estimate of at least a 20% screen failure rate between Screening and Baseline. We will monitor the actual screen failure rate to make estimates for the planned larger study to follow this one.

- First subject's first enrollment: Q1 2021
- Last subject's last encounter/call: Q2 2022

5.4 Recruitment

Figure 2 outlines the workflow of this study from recruitment to final data collection.

Recruitment

We will send out invitations to participate in CARE RA to members of the ArthritisPower registry and the Bendcare patient network via email messages in several waves. We will send out 200-400 invitations at a time and continue to send out invitations based on the response and on peer coach capacity. Bendcare will also reach out to their patients to determine their interest in this study. Bendcare will screen patients for eligibility. Eligible patients will be consented by Bendcare and transferred to the research team for randomization. Bendcare will provide access to this REDCap database used to screen and consent Bendcare patients to the WCM research team within their secure network. We will also be recruiting participants using flyers created by a company (BuildClinical). These flyers will be posted online and interested participants will be referred to us. If the patient clicks on the online flyer, they'll be prompted to complete the BuildClinical screening survey based on our eligibility criteria.

We will post a recruitment video on Twitter through the PI's professional account. The recruitment video will briefly detail the CARE RA study and invite people to fill out an interest survey through REDCap if they would like to be contacted by the research team for more information. Once an individual completes the interest survey, the research team will reach out to them.

We will further increase recruitment through the patient list of [name], [name], [name], [name], [name], and [name]. All physicians have provided our team with authorization to contact their patients whom our team will identify using EPIC. To help streamline the process of identifying patients, we will use the EHR Data and Reporting system TRAC to extrapolate patients that meet the eligibility criteria. We will not reach out to patients who marked in EPIC their wish not to be contacted for research. We will reach out to patients through doximity.

Once a person consented to participate in the study, all data collected will follow those stipulated by the study. These recruitment processes will be in place until 128 subjects are recruited.

Screening

Individuals who are interested in participating will respond to the research assistant's contact information on the invitations for ArthritisPower, the survey that Bendcare is administering, and BuildClinical flyers and corresponding survey. An unblinded research assistant from WCM will respond to direct emails from interested individuals to schedule a screening telephone call. The WCM research assistant will also call patients that have indicated on the Bendcare survey, the Twitter REDCap survey, or patients of [name], [name], [name], [name], [name], and [name] who have not marked in EPIC their wish not to be contacted for research. Before the research assistant calls the participants, they will text them from a secure number through Doximity to let them know that they will be calling them shortly. During this phone call, the study will be explained in full. Prior to any study activities, subjects will be screened for eligibility and if eligible, they will review with the unblinded WCM research assistant the Informed Consent form approved by WCM Institutional Review Board (IRB) and which complies with regulatory requirements. Subjects will be given adequate

[figure not shown]
time to consider any information concerning the study given to them by the Investigator or designee. As part of the Informed Consent process, subjects will be given the opportunity to ask the Investigator any questions regarding potential risks and benefits of participation in the study. This informed consent process will be voice recorded during the screening telephone call in the secure HIPAA protected server of WCM Division of General Internal Medicine.

Enrollment and Randomization

We will randomize subjects by a computer-generated random allocation list. The unblinded research assistant will call the subject to complete the enrollment and randomization in the study. The call will consist of the following activities:

- The subject will need to provide the date of their next appointment with their rheumatologist or other physician on their care team .
- The intervention will begin at least 6 weeks before their next appointment and the first data collection point will be at that time.
- Once a subject is enrolled and randomized, the unblinded research assistant will inform the subject the arm they have been assigned to (CARE RA vs self-administered online learning) by phone.
- During the call, the unblinded research assistant will instruct the subject on how to complete the baseline data form on the WCM REDCap that they will receive by email before initiating the intervention or at least 6 weeks before their appointment with their rheumatologist or other physician on their care team .
- During this call, all subjects regardless of arm assignment will go through a PALS tutorial with the unblinded research assistant. This training will be over the phone/Zoom by the unblinded research assistant on how to access and navigate the PALS (e.g. finding the website, searching for articles, viewing the patient-facing text, watching the videos, completing the self-assessment question for each PALS RKO). We will make available also a video tutorial on the PALS to all participants.
- All participants will receive a phone call from a blinded research assistant to make sure that they have completed all the items in the data collection form at the timepoints established for the study.
- If assigned to the CARE RA arm of the study, the unblinded research assistant will provide the subject with information about how to they will be matched with their peer coach. After the subject is matched with a peer coach, the subject will be notified that their name and phone number has been shared with their peer coach and their peer coach will be in contact with them to schedule their first call. The first call between peer coaches and subjects should occur around 5-6 weeks before their next physician appointment. Subjects will receive a copy of the CARE RA Activity Book, the Intervention Schedule, and PALS tutorial by email. A hard copy of the CARE RA Activity Book will be available upon request by the subject. The unblinded research assistant will also ensure that the subjects have received all intervention materials.
- If assigned to the self-administered online learning arm, the unblinded research assistant will provide the PALS training as described above, the curriculum of the CARE RA program in the PALS and schedule the first data collection call around 5-6 weeks before their next physician visit.

Figure 2: Diagram of the workflow of the study

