One such intervention may be peer coaching. Peer coaching interventions are gaining traction for chronic disease self-care. Peer coaches have been shown to improve medication adherence for human immunodeficiency virus (HIV), asthma, diabetes, and cancer screening.¹⁵⁻²² Peer coaches are lay individuals who themselves have the targeted chronic condition and who receive minimal training. They provide social and emotional support to the patient and could be used to help patients complete an educational program that includes decision support for CVD risk reduction strategies. However, peer coaches have not been used in RA, and have not been evaluated for CVD risk reduction in this population. Volunteer peer coaching programs are especially attractive in the context of patient communities, such as the online research community of >28,000 patients with arthritis enrolled in ArthritisPower. In preliminary discussions with my patients, several expressed interest in having contact with someone also living with arthritis to guide them through an educational program on CVD risk, ultimately helping them to discuss CVD risk reduction with their physician.

This study will use Bandura's Social Cognitive Theory to develop an online CVD risk reduction intervention for patients with RA. This theory proposed that experiential learning helps people to overcome their fears and impediments and can serve as a facilitator for behavioral change. Social support is also very important and can be achieved by interacting with others who have had similar experiences.

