7. STUDY PROCEDURES AND SCHEDULE

7.1 Intervention fidelity measures

A careful assessment of intervention implementation can provide insights into which aspects of the intervention were particularly effective. We will use several strategies to monitor intervention fidelity.

First, we will ask peer coaches to use Zoom teleconference calls for intervention delivery and record the weekly sessions between peer coaches and subjects. The goal of these recordings is to monitor fidelity of the intervention and monitor duration of the calls. These secure calls will be recorded and stored in the secure and HIPAA compliant server of the WCM Division of GIM. Study staff will review each session and use a checklist to assess intervention fidelity for each session.

Second, the peer coaches will have a checklist that they will have to complete as they go through the call of all the activities and topics that they have to cover in each session, which will ensure that these are completed by the end of each call. We will collect these checklists and compare the self-assessment of the coach to those of the study team based on their review of the Zoom call recordings. In the future larger trial, we will use these comparisons to plan for how to monitor intervention fidelity.

Third, we will monitor intervention implementation on an ongoing basis through weekly teleconferences with peer coaches, and weekly outreach to each peer coach individually throughout the intervention period. We will provide updates on the progress of the study, collaboratively troubleshoot problems, and provide ongoing advice, which often stems from other peers. At these calls, coaches will be asked to report on their clients and progress, giving the opportunity to reinforce the study protocol and MI skills.

Fourth, the research team will contact each subject twice over the 5-week intervention period to check on how the intervention is unfolding from the subject perspective.

7.2 Data collection:

All subjects will receive a baseline telephone call, the post-intervention follow up call, and the 3-month/final follow up call from the study team (Table 2). Subjects who are lost to follow-up or drop out of the study before completion will be contacted to complete the program evaluation portions of the intervention.

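### Some subjects may be treated by a study-team member who could learn which of them are coached; nothing withholds this, and no analysis sets aside subjects of study-linked physicians

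*Combined protocol and SAP*

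**What the plan says.** **Sources of subjects.** Section 5.3 opens with two networks ("We will recruit patients from the ArthritisPower Patient Powered Research Network (PPRN), the Bendcare patient network") and also names one clinical practice ("practice at New York Presbyterian"), online flyers and Twitter. Section 5.4 brings in six physicians ("We will further increase recruitment through the patient list of", names removed) and says "All physicians have provided our team with authorization to contact their patients whom our team will identify using EPIC". No split of the 128 subjects by source is given.

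**A team member with patients.** In section 2 the author writes "In preliminary discussions with my patients, several expressed interest in having contact with someone also living with arthritis". In section 4.2 a named person who helps find peer coaches "will also identify patients from her own rheumatology practice who would be suitable candidates".

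**Who produces the outcome.** Section 1 ties the primary outcome to the subject's upcoming physician appointment. Table 1 in section 4.4 accepts that a doctor may not order the test when asked.

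**Who hears about coached subjects.** Section 7.1 describes weekly teleconferences with coaches: "At these calls, coaches will be asked to report on their clients and progress". It also has study staff review recordings of the coaching sessions.

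**Safeguards.** The trial is called single-blinded. The only person described as blinded is the research assistant who follows up data collection (sections 5.4, 7.2 to 7.4 and 7.10). Section 5.4 randomizes individuals from a computer-generated list, with no stratification stated. The covariates in section 8.2 are socio-demographics, disease severity and depressive symptoms; physician, practice and recruitment source are not among them.

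**The concern.** Two distinct routes lead from a study-linked physician to the result.

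- **Dilution.** A physician who knows of the trial may test enrolled patients more readily whatever their arm. The control rate rises, the difference shrinks and power is lost. Awareness of the trial is enough.
- **Inflation.** A physician who knows the arm may test coached patients more readily without being asked. A difference then appears that coaching did not cause. This needs knowledge of the arm, and only a team member who also treats subjects has a documented route to it: coach reports and recordings exist only for coached subjects, so hearing a patient discussed reveals the arm.

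A physician who orders a test because the subject asked for it is the intended mechanism and is no bias.

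The pooled comparison would show neither effect. Section 8.1 says the pilot data will be used to design a definitive trial, and rates shaped by study-linked physicians may not carry over to physicians with no such link.

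**Working it through.** **Inputs.** From section 8.1: 80% tested in the coached arm, 60% in the control arm, 64 per arm, one-sided 5% level. Assumed, because the documents give neither: the share f of subjects whose testing depends on a linked physician (5%, 10%, 20%), and the rate r at which such physicians test them (80% or 100%).

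**Formula** (two proportions, pooled variance under the null, no continuity correction):

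Probability of a significant result = Φ{[(p₁ − p₀)√n − 1.645·√(2p̄(1 − p̄))] / √(p₁(1 − p₁) + p₀(1 − p₀))}, with p̄ the mean of p₁ and p₀.

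**The plan's own figure.** With p₁ = 0.80, p₀ = 0.60, n = 64: (0.20 × 8 − 1.645 × 0.648) / 0.632 = 0.84, and Φ = 0.801. The stated 64 per group for at least 80% power reproduces, with almost no reserve.

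**Dilution.** Linked physicians test at rate r in both arms:

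- coached rate = 0.80(1 − f) + rf
- control rate = 0.60(1 − f) + rf
- difference = 0.20(1 − f), whatever r is

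Example, f = 20%, r = 100%: 0.64 + 0.20 = 84% against 0.48 + 0.20 = 68%, a difference of 16 points.

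**Inflation.** There is no true effect (60% in both arms), and linked physicians test at rate r in the coached arm only:

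- coached rate = 0.60(1 − f) + rf
- control rate = 0.60

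Example, f = 20%, r = 100%: 68% against 60%. (0.08 × 8 − 1.645 × 0.679) / 0.676 = −0.70, and Φ = 0.241.

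| f | r | Dilution: coached / control | One-sided power | Inflation: coached / control | One-sided error |
|---|---|---|---|---|---|
| 0% | – | 80 / 60 | 80.1% | 60 / 60 | 5.0% |
| 5% | 80% | 80 / 61 | 76.7% | 61 / 60 | 6.3% |
| 5% | 100% | 81 / 62 | 77.4% | 62 / 60 | 7.9% |
| 10% | 80% | 80 / 62 | 72.9% | 62 / 60 | 7.9% |
| 10% | 100% | 82 / 64 | 74.6% | 64 / 60 | 11.9% |
| 20% | 80% | 80 / 64 | 64.7% | 64 / 60 | 11.9% |
| 20% | 100% | 84 / 68 | 68.5% | 68 / 60 | 24.1% |

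The two halves need not share the same f. For dilution, f counts subjects of any linked physician. For inflation, it counts only those whose physician knows the arm, which may be fewer.

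**Precision of an analysis without these subjects.** At f = 20%, 64 × 0.80 = 51.2, so about 51 per arm remain. The same formula at 80% against 60% gives about 72% one-sided power.

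**The case against.** **The physicians' role is largely inferred.** A reader might infer that all six listed physicians belong to the study team, order the outcome test and know the arm. The documents do not support this. Their only documented tie is permission to contact patients, and nothing places them on the coach calls. Names are removed, so their status cannot be checked either way. The link between the named practice, the author's patients and the study team is plausible but also inferred, and the section 4.2 sentence concerns recruiting coaches. This stands, and it confines the inflation route to a team member who treats subjects.

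**Being on a list does not make that physician the one who orders.** The index visit may be with a rheumatologist or another physician. The curriculum directs subjects to primary care, and section 2 says primary care physicians test lipids more often than rheumatologists. Section 3.1 also counts learning of an assessment in the past year, which needs no new order. The affected share is therefore probably below the share recruited from lists. This stands.

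**Disclosure of arm is not stated.** No text says a treating physician is told the arm; the point rests on a missing safeguard. A coached subject may also tell the physician directly, which an access rule cannot prevent. Both are fair. The rule closes only the study's own channel, but that is the channel the plan controls.

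**The size is speculative.** A reader might take 24% as the expected error. It is the corner where 20% of subjects are affected and all the coached ones are tested. The two routes act in opposite directions, so no net bias is shown, and dilution alone does not create false positives. This stands.

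**This is a modest pilot and source is partly recorded.** Section 9 uses REDCap enrolment data to count people reached through ArthritisPower. That does not show whether the physician seen or ordering is linked to the study.

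**Conclusion.** The gap is real but limited. The outcome runs through a physician's decision, some subjects may be patients of physicians linked to the study, and the plan neither withholds coaching information from a team member who treats subjects nor examines these subjects separately. Individual randomization cures neither route: dilution acts in both arms, and ordering that depends on the arm arises after allocation.

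For shares of 5–20% and testing rates of 80–100%, one-sided power falls from 80% to 65–77% under dilution. One-sided error rises from 5% to 6–24% under inflation, and only where the arm is known. Shares and testing rates are assumptions, so these figures bound what could happen and do not estimate a bias. The point merits a change to the plan because the change is cheap and the pooled result cannot reveal the problem.

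**What to change.** 1. Record for every subject the recruitment source, and whether the physician seen at the index visit or ordering the test is a study-team member or one of the listed physicians.
2. State that arm assignments, coach reports and session recordings of a physician's own patients are withheld from that physician until the final contact.
3. Prespecify in section 8.2 a supportive sensitivity analysis of the primary outcome that excludes subjects whose index or ordering physician is linked to the study.

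The cost is a small addition to data collection, an access rule and one further analysis; sample size and visits stay as they are. The sensitivity analysis is less precise than the main one and may not settle the question alone, so it should be read for direction and size beside the main result. Stratifying 128 subjects by a flag that may be rare is not required.
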